7.1 Schedule of procedures

Please see study schedule, Table 7.

- Patients will be seen by physician every week for the first cycle, every two weeks for the second cycle, at the start of each cycle after this, and at end of treatment.
- Assessment of concomitant medications at the start and during each visit.
- ECOG testing at start of treatment, at the start of physician visit and at the end of treatment.
- Blood pressure will be measured every week for the first cycle, on day 1, 7, and 14 in the second cycle, at the start of each cycle after this, and at follow up visit.
- Liver function tests [albumin, bilirubin (total), bilirubin (direct), alkaline phosphatase, GGT, AST, LDH] will be administered every week for the first cycle, every two weeks for the second cycle, at the start of each cycle after this, and at follow up visit.
- Lipase testing, electrolytes, TSH, chemistry, CEA testing, CBC, and creatinine will be done at D1 of each cycle and at end of treatment.
- A twelve-point ECG will be administered on D1 of each cycle and at the end of treatment.
- Other tests will be administered as per standard of care for regorafenib and perindopril.

The study protocol will include a patient education module. This will consist of a patient education brochure regarding the management of HFSR and will include the preventative measures patients can take to manage this side effect.

Patients will have photos of hands and feet taken at BCCA media services for illustrative purposes only, on Day 1, Day 7, Day 14 and Day 21 of the first cycle only. A total of about eight photographs per visit will be taken to capture the dorsal and plantar sides of the patient's hands and feet. The digital photographs will be labeled with your participant study number and the date. A digital copy of each photograph will be stored in the Cancer Agency Information System and a hardcopy stored in the subject study file. All photographs for the subject's study folder are to be printed with images approximately 6.25 x 9 inches on 8.5 x 11 photo paper. All photos need to be identified with study ID number and date taken.

Phase II Study of Perindopril and Regorafenib in mCRC (PARICCA)

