Methodology	
This trial will measure the incidence and severity of HFSR and hypertension in patients receiving both perindopril and regorafenib using the CTCAE v4.03 criteria.
 
The incidence of HFSR will be expressed as the number of patients out of study (N=34) who are experiencing HFSR of all grades. The incidence of hypertension will be expressed as the number of patients on study (N=34) who are experiencing hypertension of all grades. Severity will be evaluated using CTCAE v4.03 criteria as the secondary endpoint.

Type of control	This is not a randomized study. All patients in the study will receive perindopril.
Number of subjects	34 subjects, single-arm trial. A total of 38 will be recruited to allow for screen failure
Primary endpoint	To assess the incidence of all grade toxicities for HFSR.
Secondary endpoints	
Secondary Outcomes
 
 • Hypertension: All grades of hypertension will be evaluated using CTCAE v4.03, weekly for the first six weeks while they are on the study drug, then every second week and during the 30-day follow up period (Post therapy). • Toxicity: all grades of AE (including HFSR) will be evaluated using CTCAE v4.03, at baseline and at D1 of each cycle while they are on the study drug and during the 30-day follow up period (Post therapy). • Time course to development of worst grade (stage 3) HFSR. • PFS will be evaluated based on RECIST v1.1 criteria.
Plan for statistical analysis	
Statistical & Analytical Plan and Methodology
 
General considerations
 
Statistical analyses will be performed using SAS 9.3. Demographic and other baseline characteristics will be listed and summarized. Qualitative data will be summarized using frequencies and percentages and quantitative data will be summarized by appropriate descriptive statistics (mean, standard deviation, median, minimum and maximum). Secondary safety variables will be summarized using descriptive statistics and exploratory graphical presentations of the data.
 
Duration of study treatment exposure, cumulative dose and dose

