2.1 Primary outcome

Incidence of all grade toxicities for HFSR will be evaluated.

Patients will be seen by physician every week for the first six weeks, then every two weeks after (see attached study schedule, APPENDIX A).

Subjects are to be evaluated for symptoms and AEs in a visit **30 days (+7 days)** after permanently stopping study treatment. After the last contact of the Safety Follow-Up Visit (or after the EOT visit if the Safety Follow-Up Visit is not available), subjects will be off study.

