2.2 Secondary outcomes

- Hypertension: All grades of hypertension will be evaluated using CTCAE v4.03, weekly for the first six weeks while they are on the study drug, then every second week and during the 30-day follow up period (Post therapy)(see attached study schedule, APPENDIX A).

Phase II Study of Perindopril and Regorafenib in mCRC (PARICCA)

- Toxicity: all grades of AE including HFSR will be evaluated using CTCAE v4.03, at baseline and at D1 of each cycle while they are on the study drug and during the 30-day follow up period (Post therapy).
- Time course to development of worst grade (grade 3) HFSR.
- PFS will be evaluated based on RECIST v1.1 criteria, 20% progression or any new lesion.

3. Investigators and other study participants

Study sponsors and PIs:

[name], [name]
BC Cancer Agency – Vancouver Cancer Centre
[name]
[name]

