6.1 Treatments to be administered

The following investigational products will be used in this study:

- Regorafenib, 40 mg tablets
- COVERSYL® (perindopril erbumine) 4 mg.

Stivarga® will be used as per the marketed indication (“on label”), Coversyl® will be used off-label and as such a Clinical Trial Application will be filed with Health Canada.

COVERSYL® (perindopril erbumine) 4 mg will be administered daily for 21 days of a 28-day cycle. Perindopril will be administered orally, first thing in the morning on an empty stomach.

Regorafenib will be administered 160 mg daily for 21 days of a 28-day cycle. Regorafenib will be administered with low fat breakfast, one hour after perindopril. A low fat breakfast as defined by the Stivarga® (regorafenib) Product Monograph is one that is <30% fat, ~300-550 calories. See Appendix 14.4.

Table 1: Treatment Plan

Phase II Study of Perindopril and Regorafenib in mCRC (PARICCA)

Drug	Dose	Administration Guidelines
Perindopril	4 mg daily*	Administered orally on an empty stomach first thing in the morning.
Regorafenib	160 mg daily	Administered orally, one hour after waking with a low fat breakfast.

Caution with use of potassium sparing diuretics.

Caution for development of hypotension with diuretics.

BSC includes any concomitant medications or treatments: antibiotics, analgesics, radiation therapy for pain control (limited to bone metastases), corticosteroids, transfusions, psychotherapy, growth factors, palliative surgery, or any other symptomatic therapy necessary to provide BSC, except other investigational anti-tumor agents or anti-neoplastic chemotherapy.

Patients will continue study treatment until disease progression or they meet the criteria in Section 5.2. The dose modifications will follow the pre-defined dose levels outlined in Section 6.4.

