7.1.2.2 Treatment

The following assessments should be performed on the **first day of each cycle** (every 4 weeks) prior to receiving study treatment (+/- 7 days):

- The inclusion and exclusion criteria should be checked to ensure appropriate patients are treated at Day 1 of Cycle 1 only.
- Physical examination including vital signs (pulse and blood pressure), weight, temperature and examination of pertinent organ systems ECOG performance status

Phase II Study of Perindopril and Regorafenib in mCRC (PARICCA)

- Toxicity and adverse events documentation (including Start/Stop dates, seriousness, CTC notation and grading, relationship to study drug, outcome and action taken) using CTCAE v4.03
- Concomitant medications (including start/stop dates, dose, indication)
- Echocardiogram or MUGA scan only if clinically indicated. Echocardiograms or MUGA scans should be performed by the same operator to minimize inter-observer variability.

The following laboratory evaluations are not required at Day 1 of Cycle 1 if these were completed within 7 days of starting study drug treatment. Otherwise, these laboratory evaluations are required on Day 1 of each cycle:

- CBC with differential should be performed: RBC, hemoglobin, hematocrit, platelet count and WBC. WBC must include differential neutrophil, lymphocyte, monocyte, basophil and eosinophil counts. (note: BCCA lab does 5 part differentials).
- Electrolyte panel: sodium, potassium, chloride and Chemistry panel: Aspartate Amino-Transferase (AST), bilirubin (total and direct), alkaline phosphatase, triglyceride levels, uric acid, total protein, albumin, calcium, lipase, amylase, phosphate, Lactic Dehydrogenase (LDH), glucose, creatinine and Blood Urea Nitrogen (BUN)
- Thyroid function test (TSH, free T3, free T4)
- Coagulation panel: Prothrombin time (PT) or the International Ratio of PT (PT-INR) and Partial Thromboplastin Time (PTT). If a patient is on warfarin with stable PT/INR at baseline, the PT/INR should be assessed on Day 5 of Cycle 1. If either of these values is above the acceptable range, the doses should be modified and the assessments should be repeated weekly until it is stable.
- Urinalysis: appearance, pH, glucose, ketones, erythrocytes, leukocyte esterase, nitrite, bilirubin, urobilinogen, protein, creatinine, and protein/creatinine ratio. A microscopic analysis should be performed if the appearance is turbid, or if protein, leukocytes, erythrocytes or nitrite are out of normal range.

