7.1.2.3 End of Treatment Visit

When a patient is taken off treatment, the following assessments should be performed within 14 days (+/- 7 days) after study treatment has stopped:

- Brief medical history and complete physical examination including review of all organ systems, examination of pertinent organ systems, vital signs (heart rate, blood pressure and temperature) and weight
- ECOG performance status
- A CBC with differential should be performed: RBC, hemoglobin, hematocrit, platelet count and WBC. WBC must include differential neutrophil, lymphocyte, monocyte, basophil and eosinophil counts.
- Liver function tests
- CEA testing
- Creatinine
- Urinalysis: appearance, pH, glucose, ketones, erythrocytes, leukocyte esterase, nitrite, bilirubin, urobilinogen, protein, creatinine, and protein/creatinine ratio. A microscopic analysis should be performed if the appearance is turbid, or if protein, leukocytes, erythrocytes or nitrite are out of normal range.

Phase II Study of Perindopril and Regorafenib in mCRC (PARICCA)

- Quantification of proteinuria by urinary protein/creatinine ratio on a random urine sample preferably taken at mid-morning. This should be reported as the ratio of concentrations of total urine protein (in mg/dl) to urine creatinine (in g/dl).
- Measurement of GFR according to the MDRD (Modified diet in renal disease) abbreviated formula.
- 12-lead ECG
- Concomitant medications
- Toxicity and adverse events documentation
- For patients who discontinue for reasons other than disease progression, tumor measurements and evaluation of tumor response of all measurable lesions should be performed according to RECIST criteria, version 1.1.

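### From Cycle 3 the visit schedule takes blood pressure only before dosing on Day 1, so no on-drug reading is planned after Cycle 2 Day 14, although the synopsis and section 2.2 call for evaluation every second week

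*Combined protocol and SAP*

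**What the plan says.** **Outcome definition.** Section 2.2 has all grades of hypertension evaluated "weekly for the first six weeks while they are on the study drug, then every second week and during the 30-day follow up period". The synopsis gives the same frequency. Section 2.1 sets the same rhythm for physician visits: "every week for the first six weeks, then every two weeks after".

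**Visit schedule.** Section 7.1 has blood pressure taken weekly in Cycle 1 and then "on day 1, 7, and 14 in the second cycle, at the start of each cycle after this, and at follow up visit". In Table 7 the blood-pressure row is marked on Days 1, 7, 14 and 21 of Cycle 1, on Days 1, 7 and 14 of Cycle 2, once for Cycle 3 onward, and at end of treatment. Cycle 2 Day 21 and the follow-up column are blank. Section 7.1.2.2 places the Day 1 assessments, blood pressure included, "prior to receiving study treatment (+/- 7 days", and lists no mid-cycle visit after Cycle 2 Day 14.

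**Dosing.** For perindopril, section 6.1 states that "4 mg will be administered daily for 21 days of a 28-day cycle". For the partner drug: "Regorafenib will be administered 160 mg daily for 21 days of a 28-day cycle".

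**After stopping.** For the end-of-treatment visit, section 7.1.2.3 says that "the following assessments should be performed within 14 days (+/- 7 days) after study treatment has stopped".

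**Diary.** Section 7.1.2.2 has a blood-pressure diary handed out on Day 1 of each cycle. A patient who records at home is to contact the physician at 150 systolic and/or 100 diastolic and above. A reading frequency is given only for the first six weeks.

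**The concern.** The outcome definition and the visit schedule disagree about blood pressure after week 6. Sites normally work from the visit schedule, and that version also puts every later reading in the drug-free part of the cycle.

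Two things are at stake. Section 2 makes both incidence and severity of hypertension outcomes in patients receiving the two drugs. An asymptomatic rise that occurs only during dosing in Cycle 3 or later could go unrecorded, which can only lower the observed incidence or maximum grade. Symptomatic or treated hypertension would still reach the record, through the once-per-cycle adverse event and concomitant medication review.

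Table 5 also acts on mmHg values. It starts or intensifies treatment from Grade 2, holds regorafenib at Grade 3, and lets the investigator re-escalate if pressure stays controlled for a full cycle. From Cycle 3, a full cycle has no scheduled on-drug reading to support those decisions.

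**Working it through.** The plan states no figure on this point to reproduce; the check maps the two schedules onto study days.

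**Inputs.** 28-day cycles with dosing on Days 1–21 (6.1); reading days from 7.1, Table 7 and 7.1.2.2; frequency from 2.2; an expected 2–4 cycles (Table 7) or four months on trial (1.6). Nominal visit days are used. The Cycle 2 Day 14 visit has a window of 3 days either way, so it could fall as late as Day 17.

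**1. Readings in Cycles 1–2.** Study days 1, 7, 14, 21, 29, 35, 42. Days 1 and 29 are pre-dose Day 1 visits. That leaves five on-drug readings, the last on study day 42 (28 + 14).

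**2. Readings in Cycles 3–4.**
- Operational schedule: days 57 and 85, both pre-dose after Days 22–28 off drug. On drug: 0.
- Section 2.2, every 14 days: days 57, 71, 85, 99 if aligned to Day 1, or 56, 70, 84, 98, 112 if counted from day 42. On drug: 2 either way (Day 14 or 15 of each cycle).

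**3. Visit window.** The early edge for Cycle 3 Day 1 is 57 − 7 = study day 50, which is Day 22 of Cycle 2: the first day off both drugs.

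**4. Dosing days after the last on-drug reading.** Dosing days up to study day 42: 21 + 14 = 35.

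| Time on treatment | Dosing days | After day 42 | Share |
|---|---|---|---|
| 2 cycles | 42 | 7 | 17% |
| 3 cycles | 63 | 28 | 44% |
| 4 cycles | 84 | 49 | 58% |
| 4 months (121.75 days) | 84 + 9.75 = 93.75 | 58.75 | 63% |

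**5. Rough effect on the any-grade proportion** (illustrative).
- Assume time on treatment follows exponential PFS with medians of 1.9 and 3.2 months (the regorafenib figures in 1.6). Cycle 3 starts after 56 days = 1.84 months. Entering it: 34 × 2^(−1.84/1.9) = 17.4, to 34 × 2^(−1.84/3.2) = 22.8.
- Assume 25–70% already count as hypertensive by Cycle 2 Day 14. The low end is the lower of the two all-grade rates in 1.2 (28% and 25%); the high end has no source in the documents. Still able to be missed as first onset: 17.4 × 0.30 = 5.2, to 22.8 × 0.75 = 17.1.
- Assume 5–10% of these have a late onset visible only on drug (also unsourced). Missed: 5.2 × 0.05 = 0.26, to 17.1 × 0.10 = 1.7 patients. Over 34, that is 0.8 to 5.0 percentage points.

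**6. Effect of a Day 14 reading.** The longest run of dosing days without a reading falls from 21 (Days 1–21) to 13 (Days 1–13).

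**The case against.** **It is only a text conflict, since 2.2 already contains the intended schedule.** In part this stands: the protocol as a whole does not forgo on-drug readings, and the gap belongs to 7.1, Table 7 and 7.1.2.2. Sections 2.1 and 2.2 also refer to a schedule in an Appendix A, which is not among appendices 14.1–14.8; it may be an old name for Table 7. But those three places are what visits are booked from, and they agree with one another.

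**The window runs to Day 8, which is within dosing.** Read literally, yes. However, the assessment is to precede treatment, and study drug is dispensed at that visit. A late visit is therefore not a planned on-drug reading.

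**Safety is covered in other ways.** Section 4 promises continuous safety monitoring, 6.4.2 says pressures will be monitored, Table 5 suggests closer monitoring at Grade 1, and the diary has its call threshold. A Grade 3 hold ends only once diastolic pressure is 90 or below, which itself needs readings, and re-escalation is discretionary. All of this reduces the safety weight. None of it sets a reading day after week 6, and a reading such as 145/92 is Grade 2 in Table 5 but below the call threshold.

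**The effect on the endpoint is small.** Agreed. Cycles 1–2 are densely sampled, the any-grade proportion is cumulative, and Grade 1 starts at 120/80.

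**Stronger readings.** A reader might infer that hypertension goes unmonitored from Cycle 3, or that a Day 1 reading cannot detect it. The documents give no washout data, so a Day 1 reading may well show persisting hypertension; the claim is only that none is scheduled during dosing. Nor do they support the inference that the primary endpoint is compromised: HFSR does not depend on blood-pressure readings.

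**Conclusion.** The point holds as a mismatch between the outcome definition and the operational schedule. From Cycle 3 that schedule plans no on-drug blood-pressure reading, against two implied by 2.2 over Cycles 3–4. For a patient treated for three cycles or more, 44% to 63% of dosing days fall after the last planned on-drug reading. These shares apply only to those who continue: under the exponential assumption, 11 to 17 of 34 patients (34 − 22.8 to 34 − 17.4) never enter Cycle 3.

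The descriptive any-grade hypertension proportion is probably little affected, by roughly 1 to 5 points downward under assumptions that are partly unsourced. The primary HFSR test and the stopping rule are untouched. The main loss is a scheduled on-drug value for Table 5 treatment, dose-hold and discretionary re-escalation decisions. Severity: minor to moderate.

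**What to change.** 1. In 7.1, 7.1.2.2 and Table 7, add one blood-pressure reading at about Day 14 (3 days either way) of each cycle from Cycle 3, by home diary by default and in clinic if preferred. With Day 1 this meets the frequency in 2.2.
2. Have the patient phone in any Day 14 reading of 140 systolic or 90 diastolic and above, the Grade 2 boundary in Table 5. It can then be confirmed and acted on during dosing instead of waiting for the next off-drug Day 1.
3. Amend 6.4.2, which leaves recording to clinical staff, so that physician-confirmed diary readings count, as 7.1.2.2 already allows.
4. Remove the follow-up blood-pressure reading from 7.1, and word 2.2 and the synopsis to match Table 7 and 7.1.2.4, where that contact may be by telephone and covers adverse events and medications only. Point 2.1 and 2.2 to Table 7.

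Relaxing 2.2 to match Table 7 would remove the contradiction but leave no scheduled on-drug reading.

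The cost is protocol wording, a Table 7 column and a CRF field, plus one extra home reading per cycle and an occasional phone call for patients who reach Cycle 3. Requiring a clinic reading would add a mid-cycle attendance that does not now exist from Cycle 3, so it should stay optional.

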7.1.1 Tabulated overview

Table 7

Procedure	Day -28 to Day -1	Day -14 to Day -1	Day -7 to Day -1	Cycle 1				Cycle 2				Cycle 3+	End of treatment	Follow up (+1 month)
				Day1	Day7	Day14	Day21	Day1	Day7	Day14	Day21			
Medical History	x												x	
Physician Visit		x		x	x	x	x	x		x		x	x	
Concomitant Meds.		x		x	x	x	x	x	x	x		x	x	x
ECOG		x		x	x	x	x	x		x		x	x	
Blood Pressure		x		x	x	x	x	x	x	x		x	x	
Liver Function Tests			x	x	x	x	x	x		x		x	x	
12-lead ECG	x			x				x				x	x	
Cardiac Function Test*				x ¹				x ¹				x ¹		
Lipase Testing			x	x [#]				x				x	x	
PT or PT-INR and PTT			x	x [#]				x				x	x	
Full urinalysis, measure of proteinuria and GFR			x	x [#]				x				x	x	
AE				x	x	x	x	x	x	x		x	x	x
CEA			x	x [#]				x				x	x	
CBC			x	x [#]				x				x	x	
Creatinine			x	x [#]				x				x	x	
Electrolytes			x	x [#]				x				x	x	
TSH			x	x [#]				x				x	x	
Chemistry			x	x [#]				x				x	x	
hCG			x											
CT - every eight weeks	x			x								x		
Photos				x	x	x	x							

Lipase, Creatinine, Electrolytes are generally inclusive with chemistry.

34 patients, Study expected to last 2 -4 cycles

Tests will be administered as per standard of care for Regorafenib

PROTOCOL Version 2.2 Dated 08 February 2017

Phase II Study of Perindopril and Regorafenib in mCRC (PARICCA)

Weekly monitoring by physician in first cycle

* Echocardiogram or MUGA scan

¹ Echocardiogram or MUGA scan only if clinically indicated. Echocardiograms or MUGA scans should be performed by the same operator to minimize inter-observer variability.

7.1.2 Timing of assessments

7.1.2.1 Screening

The assessments required as part of Screening can be completed in one or more visits, as long as the assessments are completed within the time frames listed below.

The following procedures and assessments will be performed **within 28 days of starting study drug**:

- Obtainment of written informed consent. No screening procedures may be performed unless written informed consent has been obtained (see Section 11.2)
- Allocation of unique Study Identification Number
- Confirm pathologic documentation of a primary diagnosis of CRC.
- Radiological tumor assessment using the RECIST criteria, version 1.1 (see Appendix 14.1) must be performed. The radiological evaluation must include a CT or MRI of the chest, abdomen and pelvis and should meet the standard of care for the imaging of lesions in the respective organ system(s). A PET scan is not acceptable for radiological evaluation.
- All additional suspected sites of disease should be imaged. A CT or MRI scan of the head must be performed with appropriate contrast media if a patient is suspected of having brain metastases, or is symptomatic.
- Appropriate radiological evaluation should be obtained if bone metastases are suspected (e.g., bone scan).
- Complete medical history including demographics, allergies, prior surgery and prior chemo/radiation therapy with documentation of treatment response. See section 7.5.1.1 for detailed instructions on the differentiation between medical history and adverse events.
- Previous HFSR (or HFS) of any grade with other chemotherapy (yes/no response only, no chart review).
- 12-lead ECG

The following procedures and assessments will be performed **within 14 days of starting study drug**:

- ECOG performance status (Appendix 14.6).
- Physical examination including review of all organ systems, examination of pertinent organ systems, vital signs (heart rate, blood pressure, and temperature) weight and height.
- The blood pressure measurements must be performed in a consistent manner using a manual cuff on the same arm. Have the patient sit comfortably for 5 minutes with feet on the floor and arm supported at heart level prior to taking the evaluation. The assessment must be made with the patients in the sitting position using the same arm for all evaluations. Two additional measurements, taken 5 minutes apart, should be conducted if the first blood pressure is abnormal.

Phase II Study of Perindopril and Regorafenib in mCRC (PARICCA)

- Record of all concomitant prescribed and over-the-counter medications. All medications and significant non-drug therapies taken within 14 days before study treatment must be recorded in the CRF.

The following procedures and assessments will be performed **within 7 days of starting study drug**:

- A CBC with differential should be performed: RBC, hemoglobin, hematocrit, platelet count and WBC. WBC must include differential neutrophil, lymphocyte, monocyte, basophil and eosinophil counts.
- Electrolyte panel: sodium, potassium, chloride and Chemistry panel: Aspartate Amino-Transferase (AST), bilirubin (total and direct), Gamma GT, alkaline phosphatase, total protein, albumin, calcium, lipase, amylase, phosphate, Lactic Dehydrogenase (LDH), glucose, creatinine and Blood Urea Nitrogen (BUN).
- Thyroid function test (TSH, free T3, free T4).
- Coagulation panel: Prothrombin time (PT) or the International Ratio of PT (PT-INR) and Partial Thromboplastin Time (PTT).
- Urinalysis: appearance, pH, glucose, ketones, erythrocytes, leukocyte esterase, nitrite, bilirubin, urobilinogen, protein, creatinine, and protein/creatinine ratio. A microscopic analysis should be performed if the appearance is turbid, or if protein, leukocytes, erythrocytes or nitrite are out of normal range.
- Quantification of proteinuria by urinary protein/creatinine ratio (UPCR) on a random urine sample preferably taken at mid-morning. This should be reported as the ratio of concentrations of total urine protein (in mg/dl) to urine creatinine (in g/dl). If UPCR is outside of Normal Range (>30 g/mol Creat), then a 24-hour urine protein test should be performed to confirm Grade 3 or higher proteinuria (>3.5 g/24 hours).
- Measurement of GFR according to the MDRD (Modified diet in renal disease) abbreviated formula.
- Carcinoembryonic antigen (CEA) testing.
- A negative urine or serum pregnancy test for women of childbearing potential.
- The inclusion and exclusion criteria should be checked during the screening period to ensure appropriate patients are enrolled.

